#### **1.2.4. Rationale for Avelumab, Axitinib, and Sunitinib Starting Dosing Regimens**

##### **1.2.4.1. Avelumab and Axitinib Starting Dosing Regimens**

In Arm A, avelumab will be given in combination with axitinib. The avelumab dosing regimen will be 10 mg/kg administered as a 1-hour intravenous (IV) infusion every 2 weeks (Q2W, 3 doses in a 6-week cycle).

The axitinib starting dosing regimen will be 5 mg administered orally (PO) twice daily (BID) with or without food.

These dosing regimens have been proven to be safe and tolerable in study B9991002 (see [Section 1.2.3](#)).

##### **1.2.4.2. Sunitinib Starting Dosing Regimen**

In Arm B, the sunitinib dose will be 50 mg PO once daily (QD) continuously for 4 consecutive weeks followed by a 2-week off-treatment period (Schedule 4/2 in 6-week cycles) with or without food. This dose schedule has proven to be safe and efficacious in patients with aRCC and has been approved by regulatory authorities worldwide.

#### **1.3. Summary of Benefit/Risk Assessment**

An evaluation of the anticipated benefits and risks as required in Article 3(2)(a) of Directive 2001/20/EC (cf. Article 6(3)(b) of Directive 2001/20/EC) has been conducted.

Blocking the PD-1/PD-L1 pathway by agents binding either PD-1 or PD-L1 (anti-PD1 mAB or anti-PDL1 mAB) is a novel immunotherapeutic approach for aRCC, and anti-PD1 and anti-PDL1 agents have shown single-agent efficacy in patients whose disease has progressed following VEGF pathway inhibitor therapy. Furthermore, anti-PD1/PD-L1 antibodies have shown to produce objective response rates of 13% to 52% as single agents or in combination with a VEGF pathway inhibitor in patients with aRCC. Recent studies suggested that TKI administration induces PD-L1 expression which might lead to immune tolerance and acquired resistance to VEGF targeted agents such as axitinib. Therefore, the addition of axitinib, which is a standard therapy for patients with RCC, might lead to synergistic activity with avelumab in treating patients with aRCC.

Thus far, avelumab has demonstrated a manageable safety profile and significant anti-tumor activity in various tumor types, including aRCC (see [Section 1.2.2.1](#)).

Axitinib is approved multinationally for the treatment of aRCC after failure of one prior systemic therapy. Furthermore, axitinib has been studied as first line treatment in a Phase 3 trial and in this setting the safety profile is comparable to the ones experienced by second line patients. Overall, the adverse events reported for axitinib in clinical studies is considered tolerable and manageable, and are well characterized (see [Section 1.2.2.2](#)). Moreover, since axitinib causes less hepatic and hematologic toxicity than sunitinib, it is considered to be a better partner for pairing with other anti-cancer agents such as avelumab.

Given the occurrence in the early phases of treatment of the 2 cases described above, the study plans to monitor patients at regular intervals as described in the [Schedule of Activities](#), including MUGA/Echocardiogram, ECG, BNP, troponin and CK-MB monitoring. Moreover guidelines about the management of suspect or confirmed cases of myocarditis and relevant avelumab management instructions have been added to Table 6.

As to the anti-tumor activity of the combination, preliminary data with the combination are encouraging as 1 confirmed CR (2.6%), 19 PRs overall (15 confirmed PRs) (52.8%), 9 SDs (25%) have been reported for a objective response rate (confirmed and unconfirmed) of 55.6% (95% CI: 38.1-72.1).

As for the control arm of the study B9991003, sunitinib is approved multinationally for the first line treatment of aRCC patients. Overall, the adverse events reported for sunitinib in clinical studies are well characterized and considered tolerable and manageable. The choice of sunitinib as control treatment for the study appears therefore justified.

In conclusion, the proposed scientific rationale and the preliminary benefit-risk profile of avelumab plus axitinib observed in study B9991002 support the further investigation of the combination in the patient population chosen for this study.

## 2. STUDY OBJECTIVES AND ENDPOINTS

### 2.1. Objectives

#### Primary Objective

- To demonstrate that avelumab in combination with axitinib is superior to sunitinib monotherapy in prolonging PFS or OS in the first-line treatment of PD-L1 positive patients (patient population prospectively defined as noted in [Section 7.5.1](#)) with aRCC.

#### Secondary Objectives

- To demonstrate that avelumab in combination with axitinib is superior to sunitinib monotherapy in prolonging PFS in the first-line treatment of patients with aRCC unselected for PD-L1 expression.
- To demonstrate that avelumab in combination with axitinib is superior to sunitinib monotherapy in prolonging OS in the first-line treatment of patients with aRCC unselected for PD-L1 expression.
- To evaluate other measures of efficacy of avelumab in combination with axitinib and sunitinib monotherapy in the first-line treatment of aRCC patients.
- To evaluate progression-free survival on next-line of therapy (PFS2).
- To evaluate the overall safety profile of avelumab in combination with axitinib and sunitinib monotherapy in the first-line treatment of aRCC patients.
- To evaluate the population pharmacokinetics of avelumab and axitinib when administered in combination.
- To evaluate the time to treatment discontinuation/failure due to toxicity.
- To evaluate the proportion of patients who discontinued treatment due to toxicity.
- To evaluate candidate predictive biomarkers in pre-treatment tumor tissue that may aid in the identification of a patient subpopulation most likely to benefit from treatment with avelumab in combination with axitinib and sunitinib monotherapy.
- To assess the immunogenicity of avelumab when combined with axitinib.
- To evaluate the effects of avelumab in combination with axitinib and sunitinib monotherapy on patient-reported outcomes.

## 2.2. Endpoints

### Primary Endpoints

- Progression-Free Survival (PFS) based on Blinded Independent Central Review (BICR) assessment per RECIST v.1.1 for PD-L1 positive patients (patient population prospectively defined as noted in [Section 7.5.1](#)).
- Overall Survival (OS) for PD-L1 positive patients (patient population prospectively defined as noted in [Section 7.5.1](#)).

### Secondary Endpoints

- PFS by BICR assessment per RECIST v.1.1 for patients unselected for PD-L1 expression
- OS for patients unselected for PD-L1 expression.
- Objective Response (OR), Disease Control (DC), Time to Tumor Response (TTR) and Duration of Response (DR) based on BICR assessment and based on Investigator assessment, per RECIST v.1.1.
- Progression-Free Survival (PFS) based on Investigator assessment per RECIST v.1.1.
- Progression-Free Survival on next-line therapy (PFS2).
- Adverse events (AEs) and laboratory abnormalities as graded by National Cancer Institute (NCI) Common Terminology Criteria for Adverse Events (CTCAE) v4.03 (Appendix 6); vital signs (blood pressure, pulse rate).
- Time to treatment discontinuation/failure due to toxicity).
- Treatment discontinuation due to toxicity.

- PK parameters including trough concentrations ( $C_{\text{trough}}$ ) of avelumab and trough concentrations ( $C_{\text{trough}}$ ) and maximum concentrations ( $C_{\text{max}}$ ) of axitinib.
- Tumor tissue biomarker status (ie, positive or negative; based on, for example, PD-L1 expression and/or quantitation of tumor infiltrating CD8+ T lymphocytes as assessed by immunohistochemistry [IHC]).
- Measures of clinical outcome (PFS, OS, OR, DC, TTR, and DR) in biomarker-positive and biomarker-negative subgroups.
- Anti-drug antibodies (ADAs; nAbs) of avelumab when in combination with axitinib.
- Patient-Reported Outcomes (PRO): FACT-Kidney Symptom Index (FKSI-19), EuroQol 5-Dimension (EQ 5D).

[REDACTED]

[REDACTED]

[REDACTED]

### 3. STUDY DESIGN

#### 3.1. Study Overview

This is a Phase 3, multinational, multicenter, randomized (1:1), open-label, parallel 2-arm study in which approximately 830 patients including a minimum of 580 PD-L1 positive patients (patient population prospectively defined as noted in [Section 7.5.1](#)) are planned to be randomized to receive either avelumab in combination with axitinib or sunitinib monotherapy.

Arm A: avelumab 10 mg/kg IV Q2W in a 6-week cycle + axitinib 5 mg PO BID.

Arm B: sunitinib 50 mg PO QD on Schedule 4/2.

Patients will be stratified according to ECOG PS (0 vs. 1) and region (United States vs Canada/Western Europe vs the rest of the world).

Crossover between treatment arms will not be permitted.

### 3.1.1. Study Treatment

In Arm A, patients will receive:

- Avelumab as a 1-hour IV infusion Q2W in a 6-week cycle.
- Axitinib PO BID, with or without food, on a continuous dosing schedule.

Treatment with study drugs may continue until confirmed disease progression assessed by BICR (see [Section 5.4.4](#) for further details on treatment continuation after initial evidence of PD), patient refusal, patient lost to follow up, unacceptable toxicity, or the study is terminated by the sponsor, whichever comes first (see [Section 6.5](#) Study Withdrawal). Axitinib treatment may be adjusted by dosing interruption with or without dose reduction ([Section 5.4.6](#)). Avelumab treatment modification for drug-related toxicities, including irAEs and infusion-related AEs is described in [Section 5.4.6](#). Axitinib inpatient dose escalation may occur if relevant criteria are met (see [Section 5.4.6.1](#)).

Patients in Arm A who stop one of the two study drugs (avelumab or axitinib) for reasons other than confirmed disease progression as assessed by BICR may continue on single-agent treatment with the other drug until disease progression by BICR assessment (RECIST v.1.1), patient refusal, patient lost to follow up, unacceptable toxicity, or the study is prematurely terminated by the sponsor, whichever comes first. At the end of study, Arm A patients who are still deriving clinical benefit from study treatment will be provided with an option for continued study treatment (eg, rollover study).

Patients who stop avelumab after initial clinical benefit while on treatment and then experience radiologic disease progression by BICR assessment thereafter will be eligible for re-treatment with avelumab at the discretion of the investigator and after discussion with the sponsor's medical monitor if 1) no cancer treatment was administered other than axitinib since the last dose of avelumab, 2) the patient does not meet the safety withdrawal criteria, and 3) the trial is still open.

Patients who develop confirmed radiological disease progression by BICR assessment on study treatment but are otherwise continuing to derive clinical benefit from study treatment (see [Section 5.4.4](#)) will be eligible to continue with avelumab combined with axitinib, or single-agent avelumab, or single-agent axitinib provided that the treating physician has determined that the benefit/risk for doing so is favorable.

In Arm B, patients will receive:

- Sunitinib PO 50 mg QD on a schedule of 4 weeks on treatment followed by 2 weeks off treatment (Schedule 4/2 in 6-week cycles).

Treatment with sunitinib may continue until confirmed disease progression assessed by BICR (see [Section 5.4.4](#) for further details on treatment continuation after initial evidence of PD), patient refusal, patient lost to follow up, unacceptable toxicity, or the study is terminated by the sponsor, whichever comes first (see [Section 6.5](#) Study Withdrawal).

Patients who develop radiological disease progression assessed by BICR on sunitinib treatment but are otherwise continuing to derive clinical benefit (see [Section 5.4.4](#)) will be eligible to continue with sunitinib provided that the treating physician has determined that the benefit/risk for doing so is favorable.

Sunitinib treatment may be adjusted by dosing interruption with or without dose reduction (see [Section 5.4.6](#)).

After review of images by BICR is stopped following the final analyses for PFS performed as specified in the protocol ([Section 9.6](#)), permanent discontinuation of treatment will be performed as per investigator-assessed disease progression (see [Section 7.7](#)).

### 3.1.2. Tumor Assessments

Anti-tumor activity will be assessed by radiological tumor assessments and will be based on RECIST guidelines v. 1.1 for primary and secondary endpoints. [REDACTED]  
[REDACTED] Computerized tomography (CT) or magnetic resonance imaging (MRI) will include chest, abdomen and pelvis (CAP) at all time points. The CT and MRI scans should be performed with contrast agents unless contraindicated for medical reasons. Premedication prior contrast media administration as per local guidelines is allowed (see [Section 5.8.5](#)). Bone scintigraphy/bone scans and brain scans/head CT/MRI are also required at screening. Bone lesion(s) identified at screening by bone scan can be further assessed by CT or MRI as per local practice and subsequently re-assessed by CT or MRI as per tumor assessment schedule. If bone scintigraphy/bone scan is the preferred assessment method for bone lesion(s) as per local practice, re-assessment during study should occur every 12 weeks after randomization. Bone scan will also be repeated during study as clinically indicated (eg, patient describes new or worsening bone pain, or has increasing alkaline phosphatase level, or other signs and symptoms of new/progressing bone metastases) or at the time of complete response (CR) confirmation. Brain must be included in subsequent tumor assessments if a patient has brain metastases at screening, otherwise brain will only be evaluated when clinically indicated.

[figure not shown]
The same imaging technique used to characterize each identified and reported lesion at screening will be employed in the following tumor assessments.

Anti-tumor activity will be assessed through radiological tumor assessments conducted at screening, at 6 weeks from randomization, then every 6 weeks up to 18 months after randomization and every 12 weeks thereafter until documented confirmed disease progression by BICR assessment (see [Section 5.4.4](#) for further details on treatment continuation after initial evidence of PD) regardless of initiation of subsequent anti-cancer therapy. In addition, radiological tumor assessments will also be conducted whenever disease progression is suspected (eg, symptomatic deterioration).

The schedule of assessments should be fixed according to the calendar, regardless of treatment schedule, treatment delays or interruptions. Imaging assessments are to be scheduled using the randomization date as the reference date for all time points and are NOT to be scheduled based on the date of the previous imaging time point.

CR and PR must be confirmed with repeated imaging performed at least 4 weeks after initial documentation of response. If radiologic imaging shows progressive disease (PD), then tumor assessment should be repeated after at least 4 weeks to confirm PD. Further details are provided in [Section 5.4.4](#).

Measurable or evaluable lesions that have been previously irradiated will not be considered target lesions unless increase in size has been observed following completion of radiation therapy.

[figure not shown]

Blinded Independent Central Review (BICR) will review all radiological images. All radiographic images will be collected and objectively verified by an independent third-party core imaging laboratory as described in the Study Manual. After review of images by BICR is stopped following the final analyses for PFS performed as specified in the protocol ([Section 9.6](#)), permanent discontinuation of treatment will be performed as per investigator-assessed disease progression (see [Section 7.7](#)). After review of images by BICR is stopped, confirmation of disease progression  $\geq 4$  weeks after the PD was first noticed will no longer be required.

Post IA3, during treatment, tumor assessments will be conducted every 6 weeks from randomization up to 18 months after randomization and every 12 weeks thereafter until disease progression by investigator assessment or initiation of subsequent anti-cancer therapy, whichever is earlier (see [Section 5.4.4](#) for details on treatment continuation after initial evidence of PD).

irRECIST-defined antitumor activity will no longer be collected as per PACL dated 02 September 2019.

All patients' files and radiologic images must be available for source verification and for potential peer review.

### 3.1.3. Safety Assessments

Safety will be monitored at regular intervals throughout the study by means of laboratory tests and clinical visits as described in the [Schedule of Activities](#). However, after the first 9 months of treatment for each patient, the Sponsor in conjunction with E-DMC might consider to reduce the assessment frequency (eg, once every 1 cycle) according to the emerging safety profile of the avelumab plus axitinib combination.

### 3.1.4. Patient Outcomes

PROs will be assessed using 2 published and validated instruments: FACT-Kidney Symptom Index (FKSI)-19 and EUROQol 5-Dimension (EQ-5D).

### 3.1.5. Pharmacokinetic/Immunogenicity Assessments

Sparse plasma/serum PK/Immunogenicity sampling will be collected for axitinib, avelumab, and anti-drug antibodies (ADA). Sampling will only be done in patients randomized to Arm A. Refer to the [SOA](#) and [Section 7.3](#) for additional details of the PK collections. Samples should be obtained from the opposite arm to the one being used for avelumab IV infusion.

### 3.1.6. Biomarker Assessments

Mandatory archival and baseline (recent) tumor tissue will be collected from all patients to support investigation and, as appropriate, clinical validation of biomarkers that may predict response to treatment. End of treatment tumor tissue from a *de novo* biopsy may also be obtained unless clinically contraindicated to support investigation of mechanisms of resistance.

Biomarker assessments are described in the [Schedule of Activities](#) and in [Sections 7.5](#)

## 4. PATIENT SELECTION

This study can fulfill its objectives only if appropriate patients are enrolled. The following eligibility criteria are designed to select patients for whom participation in the study is considered appropriate. All relevant medical and non-medical conditions should be taken into consideration when deciding whether a particular patient is suitable for this protocol.

### 4.1. Inclusion Criteria

Patient eligibility should be reviewed and documented by an appropriate member of the investigator's study team before patients are included in the study.

Patients must meet all of the following inclusion criteria to be eligible for enrollment into the study:

1. Diagnosis:
  - Histologically or cytologically confirmed advanced or metastatic renal cell carcinoma with a clear cell component. Advanced RCC patients are patients affected by unresectable disease either unresectable locally advanced or metastatic disease;
  - A formalin-fixed, paraffin-embedded (FFPE) tumor tissue block from a de novo tumor biopsy obtained during screening will be required (biopsied tumor lesion should not be a RECIST target lesion). Alternatively, a recently obtained archival FFPE tumor tissue block (not cut slides from a primary or metastatic tumor resection or biopsy can be provided if the following criteria are met: 1) the biopsy or resection was performed within 1 year of randomization AND 2) the patient has not received any intervening systemic anti-cancer treatment from the time the tissue was obtained and randomization onto the current study. If an FFPE tissue block cannot be provided as per documented regulations then 15 unstained slides (10 minimum) will be acceptable (see [Section 6.1.1](#));
  - Availability of an archival FFPE tumor tissue block from primary diagnosis specimen (if available and not provided per above). If an FFPE tissue block cannot be provided as per documented regulations, then 15 unstained slides (10 minimum) will be acceptable (see [Section 6.1.1](#));
  - At least one measureable lesion as defined by RECIST version 1.1 that has not been previously irradiated.
2. Evidence of a personally signed and dated informed consent document indicating that the patient (or a legally acceptable representative, as allowed by local guideline/practice) has been informed of all pertinent aspects of the study.
3. Patients who are willing and able to comply with scheduled visits, treatment plans, laboratory tests, and other study procedures.
4. Age  $\geq 18$  years ( $\geq 20$  years in Japan).
5. Estimated life expectancy of at least 3 months.
6. ECOG PS 0 or 1.
7. No evidence of uncontrolled hypertension as documented by 2 baseline blood pressure (BP) readings taken at least 1 hour apart. The baseline systolic BP readings must be  $\leq 140$  mm Hg, and the baseline diastolic BP readings must be  $\leq 90$  mm Hg. Use of antihypertensive medications to control BP is allowed.

8. Adequate bone marrow function, including:
  - Absolute Neutrophil Count (ANC)  $\geq 1,500/\text{mm}^3$  or  $\geq 1.5 \times 10^9/\text{L}$ ;
  - Platelets  $\geq 100,000/\text{mm}^3$  or  $\geq 100 \times 10^9/\text{L}$ ;
  - Hemoglobin  $\geq 9$  g/dL (may have been transfused).
9. Adequate renal function, including:
  - Estimated creatinine clearance  $\geq 30$  mL/min as calculated using the Cockcroft-Gault (CG) equation;
  - Urinary protein  $< 2+$  by urine dipstick. If dipstick is  $\geq 2+$ , then 24-hour urinary protein  $< 2$  g per 24 hours.
10. Adequate liver function, including:
  - Total serum bilirubin  $\leq 1.5 \times \text{ULN}$ ;
  - Aspartate aminotransferase (AST) and alanine aminotransferase (ALT)  $\leq 2.5 \times \text{ULN}$ .
11. Left ventricular ejection fraction (LVEF)  $\geq$  lower limit of normal (LLN) as assessed by either multigated acquisition (MUGA) scan or echocardiogram (ECHO).
12. Serum pregnancy test (for females of childbearing potential) negative at screening.
13. Male patients able to father children and female patients of childbearing potential and at risk for pregnancy must agree to use 2 highly effective methods of contraception (see [Section 4.3.1](#)) throughout the study and for at least 90 days after the last dose of assigned treatment.

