**Footnotes for Schedule of Activities for End of Treatment and Short-/Long-Term Follow-Up periods**

- Visit Identifiers:** Acceptable time windows for performing each assessment are described in the column headers.
- End of Treatment/Withdrawal:** Obtain these assessments if not completed in the prior week, except for tumor assessments, which need not be repeated if performed within the prior 6 weeks.
- Short- and Long-Term Follow-up:** All patients will be followed for safety every 30 days ( $\pm 3$  days) through 90 days after the last dose of investigational product or until the time of initiation of new anticancer treatment. Beyond the 90 days until the end of the study, all patients will be followed every 3 months ( $\pm 14$  days) for survival, ECOG PS, and new systemic anticancer treatment within the long-term follow-up.
- Physical Examination:** Includes an examination of major body systems and weight.
- Contraception Check:** Male patients with female partner of childbearing potential and female patients who are of childbearing potential will need to affirm that they meet the criteria for correct use of 1 of the selected methods of contraception (see Section 4.3.1 for details on methods allowed). The investigator or his or her designee will discuss with the patient the need to use 1 highly effective contraception methods consistently and correctly and document such conversation in the patient's chart. In addition, the investigator or his or her designee will instruct the patient to call immediately if the selected contraception method is discontinued, or if pregnancy is known or suspected in the patient or the patient's partner. Arm B: contraception requirements/checks should be maintained for at least 49 days after the last sunitinib dose.
- Vital Signs:** Vital signs to include blood pressure and pulse rate. Blood pressure and pulse rate should be taken with the patient in the seated position after the patient has been sitting quietly for at least 5 minutes. Two blood pressure/pulse readings will be taken at least 1 hour apart at each clinic visit.
- Hematology, Blood Chemistry, and Coagulation:** Required tests are listed in Table 7. May also be performed when clinically indicated.
- Blood Chemistry:** Full chemistry panel is required at End of Treatment/Withdrawal and during short-term follow-up visits (Days 30  $\pm 3$ , 60  $\pm 3$ , 90  $\pm 3$  after the last dose). See Table 7.

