### **4.3. Lifestyle Guidelines**

#### **4.3.1. Contraception**

In this study, patients will receive avelumab (for which the teratogenic risk is currently unknown) in combination with axitinib, which has been associated with teratogenic risk or sunitinib monotherapy which has been associated with teratogenic risk.

The investigator or his or her designee, in consultation with the patient, will confirm that the patient has selected an appropriate method of contraception for the individual patient or her partner from the permitted list of contraception methods (see [Section 4.3.1.4](#)) and will confirm that the patient has been instructed in its consistent and correct use. At time points indicated in the [Schedule of Activities](#) (SoA), the investigator or designee will inform the

patient of the need to use highly effective contraception consistently and correctly and document the conversation and the participant's affirmation in the patient's chart (participants need to affirm their consistent and correct use of at least 1 of the selected methods of contraception).

Patients must agree to use at least 1 of the selected methods of contraception throughout the study and continue to do so for at least 30 days after the last dose of study treatment for patients in Arm A, and for at least 49 days after the last dose of study treatment for patients in Arm B. In addition, the investigator or designee will instruct the patient to call immediately if the selected contraception method is discontinued or if pregnancy is known or suspected in the participant or partner.

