#### **4.3.1.1. Male Participant Contraception**

Male patients with female partner of childbearing potential must agree to use a male condom during the intervention period and for at least 30 days after the last dose of study treatment for patients in Arm A, and for at least 49 days after the last dose of study treatment for patients in Arm B.

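### Inclusion criterion 13 asks for two contraceptive methods for 90 days after the last dose; the section it cites asks for at least one method for 30 or 49 days, and the schedules follow that section

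*Protocol*

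**What the plan says.** Protocol Section 4.1, criterion 13, covers men able to father children and women of childbearing potential who are at risk for pregnancy. They "must agree to use 2 highly effective methods of contraception", with a pointer to Section 4.3.1, "throughout the study and for at least 90 days after the last dose of assigned treatment". No distinction is made between arms.

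Section 4.3.1 reads differently: "Patients must agree to use at least 1 of the selected methods of contraception throughout the study". After treatment they are to continue "for at least 30 days after the last dose of study treatment for patients in Arm A"; the corresponding minimum in Arm B is 49 days.

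The subsections keep the shorter periods. Section 4.3.1.1, on men whose partner could become pregnant, says that they "must agree to use a male condom during the intervention period and for at least 30 days after the last dose of study treatment" in Arm A, or 49 days in Arm B. Section 4.3.1.2 allows a woman of childbearing potential to take part if she uses one highly effective method for the same 30 or 49 days.

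The Schedule of Activities follows Section 4.3.1. Footnote 6 (screening and treatment), footnote 5 (end of treatment and follow-up) and footnote 7 (post-IA3) all have the patient affirm correct use of one selected method and have the site counsel on the need for one. For Arm B the last two add that "contraception requirements/checks should be maintained for at least 49 days after the last sunitinib dose".

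**The concern.** A site reading the protocol finds two different obligations, and the stricter one sends the reader to a section that does not contain it.

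The matter is one of safety. Section 4.3.1 states that axitinib and sunitinib have been associated with teratogenic risk and that the risk with avelumab is not yet known. The number of methods, and how long they must be used after the last dose, should therefore be unambiguous.

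Three practical consequences follow:

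- A patient counselled as the schedule footnotes instruct can fall short of what criterion 13 required at entry.
- The follow-up contraception checks end before criterion 13's period ends, so that period is not monitored in full.
- SAP Section 6.5.2.2 reports patients who were dosed without satisfying the inclusion criteria and identifies deviations from the protocol's own criteria. Whether such a patient counts as a deviation depends on which section is applied.

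**Working it through.** No design figure is involved, so the check sets the passages side by side.

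| Source (Protocol) | Methods | After last dose, Arm A | After last dose, Arm B |
|---|---|---|---|
| 4.1, criterion 13 | 2, highly effective | 90 days | 90 days |
| 4.3.1 | at least 1 | 30 days | 49 days |
| 4.3.1.1 (men) | male condom | 30 days | 49 days |
| 4.3.1.2 (women) | 1, highly effective | 30 days | 49 days |
| Schedule, screening and treatment, footnote 6 | 1 | not stated | not stated |
| Schedule, follow-up, footnote 5 | 1 | not stated | 49 days |
| Schedule, post-IA3, footnote 7 | 1 | not stated | 49 days |

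**Size of the gap**

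- Number of methods: 2 − 1 = 1.
- Duration, Arm A: 90 − 30 = 60 days.
- Duration, Arm B: 90 − 49 = 41 days.

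**Coverage of the checks.** Both follow-up tables place contraception checks at end of treatment, at day 30, and at day 60 for Arm B only. Neither has one at day 90. Against criterion 13, the last check comes 90 − 30 = 60 days early in Arm A and 90 − 60 = 30 days early in Arm B. Against Section 4.3.1, the checks reach the end of the period in both arms. The schedules never write out 30 days for Arm A; it is implied by the position of the last Arm A check.

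**Can one patient satisfy both rules?** On number and duration, yes: Section 4.3.1 sets minima, so two methods for 90 days also meets it. The reverse fails, since one method for 30 or 49 days meets Section 4.3.1 and the schedules but not criterion 13. Two further points go beyond a stricter and a looser version of one rule:

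1. Section 4.3.1.2 is itself an eligibility statement. A woman using one highly effective method for 30 or 49 days is eligible under it, yet Section 4.1 requires every inclusion criterion to be met, and she does not meet criterion 13.
2. For men, Section 4.3.1.1 requires a condom. Condoms do not appear in the lists of highly effective methods in Section 4.3.1.4, so the type of method differs as well as the number.

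**Pregnancy tests.** The first follow-up table, as it reads, marks a test at day 90. Its footnote 11 and Section 7.1.1 list only day 30 and, for Arm B, day 60. The post-IA3 table has no day-90 test.

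**The case against.** The strongest reply is that the conflict has little practical effect. This version carries a schedule for the period after the 28 April 2020 IA3 cut-off, and Section 9.6 places the interim analyses after all patients have been randomized. No new enrolment decision should therefore turn on criterion 13. Apart from that one sentence, the text is largely uniform: Section 4.3.1, its subsections and the schedule footnotes agree with each other, and Arm B checks run past 49 days. Anyone who keeps to criterion 13 meets the Section 4.3.1 minima on number and duration. Pregnancy testing is also required whenever pregnancy is suspected. Finally, nothing statistical depends on the point: contraception is not among the per-protocol exclusions in SAP Section 4.3.1.

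Much of this stands. The effect falls mainly on patients still on treatment or in follow-up, it runs in one direction on number and duration, and it leaves the efficacy analyses untouched. The contradiction remains, however. The commitment in criterion 13 runs through the study and 90 days beyond, so it still binds those patients while sites counsel and check them against the lower requirement. The conflicting eligibility statement in Section 4.3.1.2 and the condom rule for men cannot be explained by saying that one text is simply the stricter. The consent documents are not available here, so whether they carry the same conflict is unknown.

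**Conclusion.** The concern holds. Criterion 13 and the section it cites state different contraception requirements, and the schedules follow the cited section. The difference is one method, and 60 days after the last dose in Arm A or 41 days in Arm B; for men the type of method differs too.

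It applies to men able to father children and to women of childbearing potential at risk for pregnancy. The conclusion rests only on the current protocol text and needs no assumption about rates or outcomes. It is an internal inconsistency in a safety rule and should be corrected. It has no bearing on the endpoints, type I error, power or efficacy analysis sets; its one link to the analysis is the reporting of protocol deviations. No view is taken on which number of methods or which duration is right.

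**What to change.** Reconcile criterion 13, Sections 4.3.1, 4.3.1.1 and 4.3.1.2, and the contraception footnotes of all three schedules, so that one number of methods, one definition of acceptable method (including for men) and one post-treatment period per arm appear everywhere. The choice belongs to the sponsor's clinical and safety staff.

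Then align the follow-up contraception checks with the chosen period, write that period out for both arms in the schedule footnotes, and make the pregnancy-test entries agree across the two follow-up tables, follow-up footnote 11 and Section 7.1.1. State also how patients counselled under the differing texts will be handled in deviation reporting.

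The cost is protocol wording and matching site instructions, plus consent text if it carries the same conflict. The post-IA3 schedule already provides for re-consent as applicable. No change to the statistical design or efficacy analyses is needed.
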